Breach of confidentiality may occur if unique identifiers in datasets are linked back to personal identifiers. This is highly unlikely and measures will be taken to ensure that this does not occur. Discomfort with participation is also expected to be rare and minor. Health workers may feel uncomfortable about participating and may not enjoy having their performance and counseling skills assessed, or discussing experiences in a group of colleagues and peers. Indexes and contacts may feel uncomfortable having sensitive discussions with health workers recorded, as they may be of a sensitive nature. Similarly, they may feel uncomfortable answering questions on a survey about personal information, especially about sexual or care-seeking behaviors. Should a social harm or adverse event occur as a result of study participation, this will be documented, and appropriate referrals for medical, legal, or psychosocial support will be made.

Adequacy of protection against risks

Health workers and patients will be recruited at the facility. Eligible persons will be recruited by trained research staff fluent in their native language to initiate the consent process. Research staff will go over the entire informed consent with the eligible persons and describe: the purpose of the study, the detailed procedures to be followed, the risks and benefits of participation, the duration of participation, and the steps taken to protect the participant. The eligible person will be given the opportunity to ask questions. No coercion will be placed on persons to enroll in the study. It will be explained that declining consent will not have any impact on the care they receive. Trained research staff will be trained to discuss the pros and cons of participation with all prospective participants. The consent will also inform persons that they can withdraw at any time should they change their mind. Written informed consent will be obtained from each participant and participants will be provided with a copy of their informed consent forms. Study staff will document the informed consent process. The entire consent process will be conducted in accordance with the relevant US-based institutional review board, as well as the National Health Sciences Research Committee, the local regulatory body.

To minimize the risk of breach in confidentiality, all study-related activities will occur in private locations. All health worker and patient-level datasets will contain a unique ID number and will not contain any personal identifiers. All logs connecting participants to their unique ID will be maintained separately from all data and securely stored in double-locked filing cabinets in a central office, rather than at the facility level. Individual-level data will be collected and transmitted using encrypted technologies and saved on secure password-protected servers. All audio-recorded data will be processed, coded, and verified in a timely manner. As audio-recorded data is processed, the original audio-files will be destroyed.

To protect participants against risks associated with sensitive topics, they will be reminded that the answers to their questions will be kept confidential and that this information will not be shared with anyone. If patients or health workers anticipate discomfort, they can decline consent, as participation is voluntary. If any patients or health workers experience discomfort with any aspect of participation, they can terminate their participation early and withdraw from the study. Alternatively, they can continue participation, but decline a particular activity.

Potential benefits to subjects

Health workers may gain new knowledge and skills that make them better ACT providers or enhance their counseling skills more generally. Those in the enhanced arm may enjoy participating in blended learning activities. Those in the standard arm will have access to blended learning after the end of the main trial and knowing this may be appealing. Those in both arms may enjoy discussing the ACT program with their colleagues in focus group discussions. For individual patients, they may enjoy exit interviews and reflecting on their experience in ACT. Finally, this research is designed to create generalizable knowledge and enhance ACT programs in Malawi and beyond. Some patients and health workers may experience benefits from believing that their participation may contribute to improved service delivery.

Costs/compensation

Health workers will receive the local equivalent of US\$10 as compensation for study visits. Patients will receive the local equivalent of US\$10 as compensation for their participation.

Importance of the knowledge to be gained

There is considerable potential for the proposed research to generate findings of importance. Specifically, the activities proposed are designed to enable the delivery of high-quality ACT training to scale across Malawi. This has implications not only for Malawi but also for other countries with high HIV prevalence. Results will be disseminated nationally, regionally, and internationally.

Reportable events

All serious adverse events associated with the procedures will be appropriately reported to the UNC IRB and the Malawi NHSRC according to their reporting procedures. Field staff in Malawi will be trained to complete descriptions of adverse events that will then be sent electronically to both the PI and the co-PI. Thus, adverse events will be monitored at three levels; by the Principal Investigators, by the UNC IRB and by the NHSRC. Of course, efforts will be taken to minimize the potential for adverse events. Intervention and research staff training will stress ensuring confidentiality and avoidance of negative events, and quality assurance/quality control (QA/QC) will be performed regularly to ensure adherence to proper counseling techniques. Two types of reports will be made involving the conduct of the study. Adverse Events Reports will be made using standard forms available from the relevant IRBs for adverse events associated with the study procedures or subject participation. Serious medical adverse events are unlikely. Incident Reports will also be made of any incidents involving the conduct of the trial (e.g., enrolling a participant who did not meet eligibility criteria, etc.) These reports will be made in the form of a letter or memo to the Chairs of the relevant IRBs signed by either the PI or a co-PI. All reporting form study staff to the PI, site PI, or co-PI should be made in real-time whenever possible (i.e. when the participant is still present). However, if this is not possible, a written report must be made within 24 hours.

Copies of adverse event reports will be stored at UNC and in the study offices at Tingathe. Adverse events or incident reporting in this trial has been considered in the context of several important characteristics of the study. First, this is a minimal-risk study as defined in federal regulations: “the probability and magnitude of harm or discomfort anticipated in the research are not greater in and of themselves than those ordinarily encountered in daily life or during the performance of routine physical or psychological examinations or tests.”

In addition, we will provide contact information for participants, information on how to contact the local research staff to report such events as breaches of confidentiality, HIV-related disruption of families, acts of discrimination, and physical harm. We will ask participants to return to the research site or otherwise contact research staff in order to make such reports as well as receive referrals to mitigate potential harm. This will not include identifying information about the study or references to HIV or HIV testing, so that the cards will not have the potential to jeopardize the confidentiality of participants.

Dissemination of results

The results of the study will be presented at international and local scientific meetings and published in scientific journals. The results will also be submitted to the NHSRC. The information collected in this study may lead to larger cluster randomized trials that will allow further evaluation of the impact of blended learning modalities for training health workers in voluntary assisted contact tracing.

Work plan and Timeline

The timeline below depicts planning, implementation, data collection, data analysis, manuscript preparation, and stakeholder engagement during the full research period.

The study is divided into three phases (preparation, implementation, and analysis/dissemination) that occur over a three-year period (Table 1). The first six months of the study reflect a planning phase. Trial implementation and analysis will occur over the next 2-year period. The final six months of the study will be dedicated to analysis and dissemination and providing technical assistance to support scale-up.

Timeline

Activity	Year 1				Year 2				Year 3			
	1	2	3	4	1	2	3	4	1	2	3	4
Calendar Quarter												
Finalize intervention for enhanced arm	x	x										
Site selection	x											
Site/community sensitization	x	x										
Data training harmonization		x										
Randomization		x										
Standard training (both arms)		x										
Enhanced implementation activities (enhanced arm, n=11 sites)			x	x	x	x	x	x	x	x	x	
Standard implementation activities (standard arm, n=22 sites)				x	x	x	x	x	x	x	x	
Delayed implementation of enhanced activities (standard arm, n=22 sites)						x	x					
Technical assistance to support scale up												x
Data collection			x	x	x	x	x	x	x	x	x	
Adoption			x	x	x	x	x	x	x	x	x	
Fidelity assessments			x	x	x	x	x	x	x	x	x	
ACT data abstraction from registers			x	x	x	x	x	x	x	x	x	
Feasibility/acceptability			x		x				x			
Time and motion			x		x				x			
Annual facility surveys			x				x					
Analysis						x	x			x	x	
Manuscript development			x					x	x			x
Local/international presentations			x		x							x

Bibliography

1. Joint_United_Nations_Programme_on_HIV/AIDS_(UNAIDS). *UNAIDS Data 2019*. 2019.

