Machinga and Balaka Districts contain 34 facilities. Two small comparable facilities will be combined to create a total of 33 clusters (a number divisible by 3) to achieve 2:1 randomization. The clusters will be classified into strata of sizes 3, 6, or 9 based on key cluster-level characteristics, including district, facility type (hospital, health center, dispensary), and baseline performance (number of indexes identified) to help ensure balance of facility characteristics between the arms. Within each stratum, clusters will be randomly assigned in a 2:1 ratio to the standard or enhanced arms for the cluster RCT period (quarters 1-4). The facilities and their staff will not be blinded to study arm. However, on certain measures, such as audio-recorded fidelity assessments, coders will be blinded to randomization arm. The randomization schedule will be created by an independent statistician using a random number generator in SAS or comparable program.

Evidence based practice

In implementation science, an important first step is clear identification of the evidence-based practice, which in this case is ACT. In the Malawian context, ACT is a voluntary service which consists of offering support to HIV-positive clients to recruit sexual partners and family members for HIV testing. ACT is simple in theory, but complex in practice. Indexes may be adults or children, newly diagnosed or already on treatment. Adult contacts may be

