Outcomes of interest: Five ACT service uptake outcomes will be measured from index and contact registers on a quarterly basis. Each of these outcomes will be measured as a count per cluster per calendar quarter (three-month period). We will use facility-level data because the facility (i.e. cluster) is the primary unit of randomization. With 33 clusters under observation for four quarters, the facility-level dataset for the primary analyses will contain 132 observations (33 clusters * 4 quarters), 44 observations in the enhanced arm and 88 observations in the standard arm. The full two-year analyses will contain 264 observations (33 clusters * 8 quarters). The following measures will be calculated on a quarterly basis:

- **Total potential indexes:** This is the total number of ART and HTS patients that should be screened for and potentially offered ACT.
- **1: Indexes who participate in ACT:** The number of indexes in the index register.
- **2: Number of contacts elicited:** The number of contacts listed by the participating indexes. Are they put into the index register here?
- **3a: Number of self-test kits distributed:** The number of HIV self-test kits given to indexes for secondary distribution. Often, this is used as a method for testing contacts, rather than presenting to the clinic.
- **3b: Number of contacts tested:** The number of contacts with a recorded HIV test result. These tests are typically performed by a health care worker.
- **4: Number of contacts diagnosed HIV-positive:** The number of contacts in the contact register with an HIV-positive test result.

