Analyses: Data from quarters 1 through 4 (the cluster RCT design) will be analyzed using a negative binomial mixed-effects model accounting for quarterly repeated measures within each cluster. Models will use a log link, contain terms for randomization arm, and the natural-log transformed number of potential indexes will be incorporated as an offset term. Key baseline variables of interest, such as district, will be adjusted for. Rate ratios and 95% confidence intervals will be used to estimate the effect sizes and quantify the precision of effect estimates for the main analyses which will compare the enhanced versus standard arms for rates of each service uptake outcome per the total number of potential indexes (5 main endpoints denoted above). Secondary endpoints will take the same approach and use a negative binomial mixed effects model as well. Several secondary endpoints are proportion measures; for those endpoints effect size will be measured using a risk ratio and corresponding 95% confidence interval comparing the enhanced versus standard arms. To assess maintenance, interaction terms between quarters and randomization arm will be included to assess whether effects remain constant, intensify, or diminish over time during quarters 1 through 6.

Statistical power assumption, models, and estimates: Sample size calculations were guided by data from the 33 proposed clusters in the two districts from 2019-2020. In these two districts (Machinga and Balaka), Tingatthe supports 34 MOH facilities with implementation of the national HIV program and supervises approximately 150 community health workers and 100 HIV diagnostic assistants. Two nearby facilities in Balaka will be combined for analysis such that the 34 facilities are handled as 33 clusters.

Across these 33 clusters, 4600 persons are diagnosed with HIV each year and another 49,000 are already taking ART. From this, we estimated 35 new HIV-positive diagnoses per cluster per quarter and 372 ART patients per cluster per quarter or approximately 407 total potential indexes per facility per quarter. On average, of these 407 total potential indexes, there were approximately 86 indexes identified (0.21), 97 contacts elicited (0.24), 12 self-test kits distributed (0.03), 25 contacts tested (0.06), and 3 contacts diagnosed as HIV-positive (0.007). These values informed our assumptions for the standard arm.

Power for primary analyses:

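### Strata use a baseline count of indexes, while the five main Aim 2 endpoints are rates per potential index; stratify on the baseline rate and adjust for it

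*Combined protocol and SAP*

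**What the plan says.** The Randomization section groups the 33 clusters: "The clusters will be classified into strata of sizes 3, 6, or 9 based on key cluster-level characteristics". The characteristics named are district, facility type and "baseline performance (number of indexes identified) to help ensure balance of facility characteristics between the arms". Allocation follows within strata: "Within each stratum, clusters will be randomly assigned in a 2:1 ratio to the standard or enhanced arms".

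In the Aim 2 section, under Analyses, the main comparison is of "rates of each service uptake outcome per the total number of potential indexes", from a negative binomial mixed model in which "the natural-log transformed number of potential indexes will be incorporated as an offset term". Quarters 1-4 supply "44 observations in the enhanced arm and 88 observations in the standard arm". The model is to adjust for key baseline variables, with district as the only example. Neither a baseline rate nor the randomization strata are named.

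Under Power for primary analyses, facility-specific mean numbers of potential indexes are said to have been estimated from the background data. No spread of facility size is reported, and no gain from stratification is mentioned.

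**The concern.** The number of indexes a facility identifies is its number of potential indexes multiplied by its rate. The offset already takes size out of the main endpoints, so balancing the arms on size does little for the rate ratio. What does affect it is persistent variation between facilities in the rate. The chosen stratifier measures that variation only with size mixed in, and facility type already carries part of the size information.

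With 11 against 22 clusters, this variation is the larger part of the error for four of the five main endpoints. A stratifier closer to the rate would reduce chance imbalance. Naming the baseline rate in the model would turn the information into precision. The plan as written secures neither.

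**Working it through.** **Inputs from the Aim 2 power table.** Random intercept variance (RIV) and scale for indexes are 0.0981 and 0.0854, and the rates are 0.3100 and 0.2113. The RIV is 0.1268 for contacts elicited, 0.0001 for self-test kits, 0.3340 for contacts tested and 0.3334 for HIV-positive contacts. There are 11 and 22 clusters, four quarters, and 407 potential indexes per cluster per quarter. Alpha is 0.05, taken as two-sided.

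**Assumed, because the documents do not give them.** SD of log facility size 0.2-0.8; correlation of log size with log rate -0.5 to +0.5; the number of clusters in each district-by-type cell; a baseline of about three quarters.

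**Step 1: reproduce the stated power for indexes.** Cluster variance = RIV + (scale + 1/mean count)/4.

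- Enhanced: 0.0981 + (0.0854 + 1/126)/4 = 0.1214
- Standard: 0.0981 + (0.0854 + 1/86)/4 = 0.1224
- SE of the log rate ratio = √(0.1214/11 + 0.1224/22) = √0.01660 = 0.129
- ln(0.3100/0.2113) = 0.383
- Power = Φ(0.383/0.129 − 1.96) = 84.5%; the plan states 85%

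The same formula gives 81.1% for elicited (stated 81%), 84.8% for tested (85%) and 83.7% for HIV-positive (82%). For self-test kits it gives 86.3% against 82%. The closed form is rough when the scale is 1.9077, so that gap is not evidence of an error. The formula contains no stratification gain, so the stated power does not depend on one.

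**Step 2: chance imbalance under simple randomization.** SD of the arm difference in log rate = √(RIV × (1/11 + 1/22)). Its share of the error is its square divided by SE².

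| Endpoint | SD | 95% range as a rate ratio | Share of SE² |
|---|---|---|---|
| Indexes | 0.116 | 0.80-1.25 | 81% |
| Contacts elicited | 0.131 | 0.77-1.29 | 72% |
| Contacts tested | 0.213 | 0.66-1.52 | 81% |
| HIV-positive contacts | 0.213 | 0.66-1.52 | 72% |
| Self-test kits | 0.004 | 0.99-1.01 | under 0.1% |

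This imbalance is already inside the SE. It is not an additional error.

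**Step 3: how much of the count is rate.** log count = log size + log rate. If size and rate are independent and sampling noise is ignored, the rate's share of the variance of the log count is 0.0981/(0.0981 + s²), where s is the SD of log size. The share is 71% at s = 0.2, 50% at s = √0.0981 = 0.31 and 13% at s = 0.8. At s = 0.31 the middle 95% of facilities span exp(2 × 1.96 × 0.31), about 3.4-fold.

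**Step 4: simulate the strata the plan would keep.** District-by-type cells were imposed first (assumed layouts 3/12/3/12/3 and 6/12/3/9/3). Within each cell, clusters were sorted on the baseline count or the baseline rate, cut into strata of three or six, and randomized. Reduction in the SD of the imbalance in log index rate, relative to 0.116:

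- strata on the rate: about 15-26%, so an SD of about 0.099 down to 0.086;
- strata on the count: roughly 0-25%, so about 0.116 down to 0.087. The best case has a small size spread and a positive correlation with the rate; the worst has a negative correlation.

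Within simulation error, rate strata were never worse than count strata. A further assumed layout with zero correlation left 0.64-0.72 of the imbalance variance with rate strata and 0.72-0.98 with count strata. As SD reductions these are 15% to 20% (1 − √0.72 and 1 − √0.64) against 1% to 15%.

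**Step 5: power once the model uses the information.** Put a fraction f of the index RIV into Step 1:

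- f = 1: SE 0.129, power 84.5%
- f = 0.8 (RIV 0.0785): SE 0.118, power about 90%
- f = 0.7 (RIV 0.0687): SE 0.112, power about 93%

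The values of f are illustrations. The documents do not say how well the 2019-2020 rate predicts the trial rate.

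**The case against.** Several points on the other side stand.

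- **The gain from re-stratifying is modest.** A reader might infer that the count leaves most of the imbalance in place and that the rate would halve it. Sorting all 33 clusters on the rate alone into 11 triplets does lower the SD from 0.117 to 0.060, or 49%. But the plan also stratifies by district and facility type, and the fix keeps both. Inside those cells even rate strata leave most of the imbalance.
- **It is not shown that the count mainly ranks facilities by size.** That needs the spread of size within facility type and its correlation with the rate. With a small spread and a positive correlation, count and rate perform about equally.
- **The point does not reach every Aim 2 endpoint.** The additional cascade endpoints use the previous step as denominator, and three are proportions. Self-test kits have almost no persistent rate variation to balance.
- **The performance stratum is not the only protection.** District and facility type may carry some information on the rate, and the open-ended wording on adjustment does not exclude baseline performance.
- **Volume is a legitimate thing to balance.** The stated aim is balance of facility characteristics in a three-aim trial, and Aim 3 evaluates costs per facility.
- **The historical denominator may be uneven.** Data harmonization is scheduled for quarter 0, the quarter of randomization, so background rates predate it.

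None of this makes the count the better measure of performance for a rate endpoint, and facility type would still cover part of volume. The open adjustment wording permits the right covariate but does not commit to it.

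**Conclusion.** The mismatch is in the text: the performance stratifier is a count, and the five main Aim 2 endpoints are rates. The consequence is avoidable chance imbalance and lost precision for four of the five. It is not bias. A reader might infer that the randomization is flawed or the power overstated. Neither follows, because allocation is random within strata and the stated index power reproduces with no stratification gain.

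For the index rate, the improvement from re-stratifying is about 15-26% off the SD of the imbalance, against roughly 0-25% for the count. This rests on assumed cell layouts, log-size SD 0.2-0.8 and correlation -0.5 to +0.5. Re-stratifying alone would leave the model's SE largely unchanged. The gain in power comes only when the baseline rate and strata are in the model, and its size depends on how much random intercept variance they explain. This is a cheap improvement, not a defect that threatens the trial.

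**What to change.** 1. In the Randomization section, define baseline performance as indexes identified divided by total potential indexes over the same background months. Form the strata of 3, 6 or 9 on that rate within district and facility type.
2. Whether or not the list is already drawn, prespecify the log baseline rate and the randomization strata as covariates in the Aim 2 models. State how the strata enter: strata of three throughout would mean 11 strata and 10 parameters for 33 clusters.

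**Cost.** One phrase, one division per cluster and one sentence in the analysis section. The facility-specific denominators are described as already estimated for the power simulation. If the list is drawn, only the second change applies. The downside is that volume is then balanced only through facility type, and that the background denominator predates harmonization and should be checked for comparability across facilities before it is used.
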